12.4 IND Annual Reports

In accordance with regulation 21 CFR § 312.33, the sponsor-investigator with assistance from the MCC Clinical Trials Office (CTO) will submit a progress report annually. The report will be submitted within 60 days of the anniversary date that the IND went into effect.

12.5 Monitoring

The investigator will permit study-related monitoring, audits, and inspections by the sponsor-investigator and/or sponsor/investigator designee, IRB, government regulatory bodies, and University of Minnesota compliance groups. The investigator will make available all study related documents (e.g. source documents, regulatory documents, data collection instruments, study data, etc.). The investigator will ensure the capability for inspections of applicable study-related facilities (e.g. pharmacy, diagnostic laboratory, etc.) will be available for trial related monitoring, audits, or regulatory inspections.

12.6 Teleconferences – Lead Site and Affiliate Site

Regular teleconferences to facilitate communication between participating sites regarding the study's progress, patient updates, summary of safety reports, case report form completion, and other issues for discussion. The University of Minnesota Affiliate Manager will be responsible for arranging these teleconferences and preparing the agenda. Meetings will occur at least every 3 weeks; however, these may be scheduled more or less frequently at the discretion of the lead institution. Participation of a minimum of one representative from each affiliate site will be required. These teleconferences are in addition to other previously described site interactions including centralized patient registration, institutional and MCC required reporting of safety related issues, case report form completion in the study's central database (OnCore) and affiliate oversight through self-monitoring in compliance with the Masonic Cancer Center's Data and Safety Monitoring plan.

12.7 Affiliate Site Monitoring

The PI ([name]) with the CTO has oversight responsibility for trial monitoring at affiliate sites. Affiliate sites must self-monitor following the University of Minnesota Masonic Cancer Center Data and Safety Monitoring

Plan (DSMP - <http://z.umn.edu/dmsp>) and the CTO Affiliate and Satellite Site Monitoring SOPs.

The investigator will permit study-related monitoring, audits, and inspections by the study's Principal Investigator or any designees, the local IRB, government regulatory bodies, and University of Minnesota compliance groups. The investigator will make available all study related documents (e.g. source documents, regulatory documents, data collection instruments, study data, etc.). The investigator will ensure the capability for inspections of applicable study-related facilities (e.g. pharmacy, diagnostic laboratory, etc.) will be available for trial related monitoring, audits, or regulatory inspections.

12.8 Record Retention

The investigator will retain study records including source data, copies of case report form, consent forms, HIPAA authorizations, and all study correspondence in a secured facility for at 6 years after the study file is closed with the IRB and FDA.

In addition, the Clinical Trials Office (CTO) will keep a master log of all patients participating in the study with sufficient information to allow retrieval of the medical records for that patient.

Please contact the CTO before destroying any study related records.

13 Statistical Considerations

13.1 Study Design

This is a multi-center phase I/II study of supplemental hCG as an adjunct to facilitate improved mucosal healing and immune tolerance in conjunction with accepted, standard immunosuppressive therapy in the setting of high-risk (Arm 1), steroid-dependent (Arm 2A) aGVHD and steroid-refractory (Arm 2B). Once the MTD is identified, the objective will be to confirm safety and obtain preliminary estimates of the primary trial endpoint defined as complete response (CR) and partial response (PR) at day 28.

Phase I component: Estimating the MTD of hCG for Arm 1 and Arm 2A

The first phase is a dose finding study. The dose escalation will be two independent processes with CRM for Arm 1 (high-risk aGVHD) and Arm 2A (steroid-dependent aGVHD). The target toxicity rate was determined based on clinical input and acceptability. Continual reassessment method (CRM)

is originally proposed by O'Quigley et al [31]. The goal for CRM is to identify the dose level which corresponds to the desired toxicity rate of 25% or less. We are choosing a lower target toxicity than would be chosen under the standard design. A standard “3+3” design will often choose a dose with corresponding to a toxicity rate of 33% or lower. The trial will stop if the posterior probability (that the lowest dose is more toxic than the target dose) is 0.90.

Dose Level	hCG Dose
-2**	125 USP hCG/875 pg EGF/m ²
-1*	250 USP hCG/1,750 pg EGF/m ²
1	500 USP hCG/3,500 pg EGF/m ²
2	1,000 USP hCG/7,000 pg EGF/m ²
3	2,000 USP hCG/14,000 pg EGF/m ²

*Dose level -1 (250 USP hCG/1,750 pg EGF/m²) will be used only if Dose Level 1 (500 USP hCG/3,500 pg EGF/m²) proves too toxic.

**Dose level -2 (125 USP hCG/875 pg EGF/m²) will be used only if Dose Level -1 (250 USP hCG/1,750 pg EGF/m²) proves too toxic.

Initial estimates of toxicity or the “skeleton” estimates are given by the clinicians. The estimates of toxicity for Arm 1 and Arm2 are listed as 1%, 2%, 5%, 10% and 20% for the 5 dose levels, respectively. The 1st 2 patients will be enrolled in dose level 1.

The next cohort of 2 patients will not begin treatment until the last patient in the current cohort has reached day 21. Each new cohort of 2 patients will be assigned by the study statistician ([name] email: [contact]). The CRM assumes the working dose-toxicity model or power model. The probability (toxicity at d_i) = $p_i^{\exp(\alpha)}$ for each dose level i . The parameter α is distributed a priori as a normal random variable with mean 0 and variance 2. After simulation, a variance of 2 was predicted to balance both patient safety and accuracy. Pre-specified constants p_i for each dose are 1st determined by using the skeleton estimates at the beginning of the trial. After initiation of the trial and collection of events, the unknown parameter α is continuously updated. Calculation of posterior means of probability of toxicity from dose level i are calculated from Bayes theorem using the likelihood function based on a binomial distribution for the binary outcome of toxicity. After calculation of these means, each new cohort is assigned to the dose with an estimated toxicity probability closest to the pre-specified target toxicity of 25%.

Eventually the MTD will be identified when the total sample size of 20 patients is exhausted.

The dose limiting toxicity (DLT) is defined as any of the following occurring by day 21 after the 1st dose of hCG.

- In males and females: Grade 2-4 thromboembolic event (CTCAE v4)
- In males and females: Grade 3-4 ascites (CTCAE v4)
- Specific to females: Ovarian hyperstimulation syndrome, defined as the rapid development of enlarged, cystic, painful ovaries

Software within the BMA-CRMSimulator Version 2.1.0, downloaded from the MD Anderson biostatistics department website, will be used to calculate the posterior means of the toxicity probabilities for all of the doses under consideration:

<http://biostatistics.mdanderson.org/SoftwareDownload>. Dose escalation of more than one level is not permitted with this design.

Phase I component: Estimating the MTD of hCG for Arm 2B

The phase I design for Arm2B (steroid-refractory aGVHD) is similar to Arm 1 and Arm 2B. The goal for CRM is to identify the dose level which corresponds to the desired toxicity rate of 30% or less. We are choosing a lower target toxicity than would be chosen under the standard design. A standard “3+3” design will often choose a dose with corresponding to a toxicity rate of 33% or lower. The trial will stop if the posterior probability (that the lowest dose is more toxic than the target dose) is 0.90.

Dose Level	hCG Dose
-2**	125 USP hCG/875 pg EGF/m ²
-1*	250 USP hCG/1,750 pg EGF/m ²
1	500 USP hCG/3,500 pg EGF/m ²
2	1,000 USP hCG/7,000 pg EGF/m ²
3	2,000 USP hCG/14,000 pg EGF/m ²
4	3,500 USP hCG/24,500 pg EGF/m ²
5	5,000 USP hCG/35,000 pg EGF/m ²

*Dose level -1 (250 USP hCG/1,750 pg EGF/m²) will be used only if Dose Level 1 (500 USP hCG/3,500 pg EGF/m²) proves too toxic.

**Dose level -2 (125 USP hCG/875 pg EGF/m²) will be used only if Dose Level -1 (250 USP hCG/1,750 pg EGF/m²) proves too toxic.

Initial estimates of toxicity or the “skeleton” estimates are given by the clinicians. The estimates of toxicity for Arm 1 and Arm2 are listed as 1%, 2%, 5%, 10%, 15%, 20% and 25% for the 7 dose levels, respectively. The 1st 2 patients will be enrolled in dose level 1. The next cohort of 2 patients will not begin treatment until the last patient in the current cohort has reached day 21. Each new cohort of 2 patients will be assigned by the study

statistician ([name] email: [contact]). With same calculation described in Arm 1 and Arm 2A, each new cohort is assigned to the dose with an estimated toxicity probability closest to the pre-specified target toxicity of 30%. DLT has the same definition as the other two arms.

Operating Characteristics for Phase I (Arm 1 and Arm 2A)

Operating characteristics are calculated by BMA-CRMSimulator for two different scenarios, one in which the “true” probabilities of DLTs are the same as those specified by the clinicians and one in which the “true” probabilities of DLTs are much higher than expected. [Table 2](#) shows that there is a 88% chance of selecting the maximum dose of 2,000 USP hCG/14,000 pg EGF/m², which is closest to our target toxicity of 25%. [Table 3](#) shows that there is a 11% chance of stopping the study or a 28% chance of selecting the dose associated with a 25% toxicity rate.

Table 2. Simulations based on “true” probabilities equal to initial skeleton estimates.

Dose	Actual probability in theory of having a DLT at each dose	Probability of Selecting the specified dose given the probabilities of having a DLT listed in the 2nd column	Estimated Number of subjects treated at each dose level during the study
125 USP hCG/875 pg EGF/m ²	0.01	0.00	0.2
250 USP hCG/1,750 pg EGF/m ²	0.02	0.00	0.3
500 USP hCG/3,500 pg EGF/m ²	0.05	0.01	2.9
1,000 USP hCG/7,000 pg EGF/m ²	0.10	0.11	3.9
2,000 USP hCG/14,000 pg EGF/m ²	0.20	0.88	12.7

Table 3. Simulations based on “true” probabilities equal to excessively high toxicity.

Probability of stopping: 11%

Dose	Actual probability in theory of having a DLT at each dose	Probability of Selecting the specified dose given the probabilities of having a DLT listed in the 2nd column	Estimated Number of subjects treated at each dose level during the study
125 USP hCG/875 pg EGF/m ²	0.20	0.29	6.2
250 USP hCG/1,750 pg EGF/m ²	0.25	0.28	3.7
500 USP hCG/3,500 pg EGF/m ²	0.35	0.22	5.2
1,000 USP hCG/7,000 pg EGF/m ²	0.45	0.09	2.3
2,000 USP hCG/14,000 pg EGF/m ²	0.55	0.01	1.0

Operating Characteristics for Phase I (Arm 2B)

Operating characteristics are calculated by BMA-CRMSimulator for two different scenarios, one in which the “true” probabilities of DLTs are the

same as those specified by the clinicians and one in which the “true” probabilities of DLTs are much higher than expected. [Table 4](#) shows that there is a 78% chance of selecting the maximum dose of 5,000 USP hCG/35,000 pg EGF/m², which is closest to our target toxicity of 30%. [Table 5](#) shows that there is a 11% chance of stopping the study or a 29% chance of selecting the dose associated with a 30% toxicity rate.

Table 4. Simulations based on “true” probabilities equal to initial skeleton estimates.

Dose	Actual probability in theory of having a DLT at each dose	Probability of Selecting the specified dose given the probabilities of having a DLT listed in the 2nd column	Estimated Number of subjects treated at each dose level during the study
125 USP hCG/875 pg EGF/m ²	0.01	0.00	0.2
250 USP hCG/1,750 pg EGF/m ²	0.02	0.00	0.0
500 USP hCG/3,500 pg EGF/m ²	0.05	0.00	2.3
1,000 USP hCG/7,000 pg EGF/m ²	0.10	0.02	2.9
2,000 USP hCG/14,000 pg EGF/m ²	0.15	0.07	3.1
3,500 USP hCG/24,500 pg EGF/m ²	0.20	0.14	2.9
5,000 USP hCG/35,000 pg EGF/m ²	0.25	0.78	8.6

Table 5. Simulations based on “true” probabilities equal to excessively high toxicity.

Probability of stopping: 11%

Dose	Actual probability in theory of having a DLT at each dose	Probability of Selecting the specified dose given the probabilities of having a DLT listed in the 2nd column	Estimated Number of subjects treated at each dose level during the study
125 USP hCG/875 pg EGF/m ²	0.25	0.28	6.7
250 USP hCG/1,750 pg EGF/m ²	0.30	0.29	3.1
500 USP hCG/3,500 pg EGF/m ²	0.40	0.23	5.3
1,000 USP hCG/7,000 pg EGF/m ²	0.50	0.07	2.6
2,000 USP hCG/14,000 pg EGF/m ²	0.60	0.02	0.7
3,500 USP hCG/24,500 pg EGF/m ²	0.70	0.00	0.2
5,000 USP hCG/35,000 pg EGF/m ²	0.75	0.00	0.1

Phase II extension: Studying the efficacy of hCG (Arm 1, Arm 2A and Arm 2B)

After completion of the dose finding trial for each arm, the final doses will be carried forward into a two-stage phase II extension trial to confirm safety and make a preliminary determination of the activity level for Arm 1 and Arm 2. If the phase I trial enrolls fewer than 13 patients at the MTD, we will employ Simon’s Minmax two-stage design (Simon, 1989) with the possibility to discontinue after the 1st stage if the response rate is low.

- **Stage 1:** Enroll a total of 12 patients (including all treated at the MTD in phase I). *If 5 or more of these respond, the trial will continue to stage 2.*

- **Stage 2:** Enroll an additional 14 patients. *If 14 or more out of 26 patients respond, hCG will be considered promising for further investigation.*

If phase I trial enrolls more than 12 patients at the MTD, we will adjust the futility rule above for the two stage design with the giving number of patients enrolled at the MTD.

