- Active or recent (within prior 3 months) thrombus, irrespective of anticoagulation status
- Pregnancy
- Women or men of childbearing potential unwilling to take adequate precautions to avoid unintended pregnancy from the start of protocol treatment through 28 days after the last treatment

Enrollment Plan: Phase I: Up to 20 patients in each arm with an estimated 2 years to accrue patients
Phase II component (for each arm):
Stage 1: Enroll a total of 12 patients (including all treated at the MTD in phase I). If 5 or more of these respond, the trial will continue to stage 2.

Stage 2: Enroll an additional 14 patients. If 14 or more out of 26 patients respond, hCG will be considered promising for further investigation.

***NOTE: Arm 2B, dose level 5: to avoid using vials from more than one Lot of study product, the maximum dose is either (1) the contents of a single 10,000 IU vial, or (2) a maximum dose of 10,000 IU from multiple vials. All vials used should be from the same Lot.**

Arm 1, Arm 2A and Arm 2B will be treated as separate, independent cohorts. Each lot of Pregnyl® will be tested for EGF content prior to administration so that the precise EGF dose administered is known.

Phase I:

For each arm, dose levels of Pregnyl® will be tested starting at dose level 1. Dose levels -1 and -2 will be used only if dose level 1 proves too toxic.

The 1st 2 patients will be enrolled in dose level 1. The next cohort of 2 patients will not begin treatment until all patients in the current cohort have reached day 21. Each new cohort of 2 patients will be assigned by the study statistician to the most appropriate dose level based on toxicity probabilities set for this study. The MTD for each arm (high-risk and steroid-refractory aGVHD) will be identified at or before the total sample size of 20 patients per arm is reached.

The dose limiting toxicity (DLT) is defined as any of the following occurring by day 21 after the 1st dose of Pregnyl®:

- In males and females: Grade 2-4 thromboembolic event (CTCAE v4) i.e., any thrombosis more severe than a superficial venous thrombosis where treatment is required
- In males and females: Grade 3-4 ascites (CTCAE v4)
- Specific to females: Ovarian hyperstimulation syndrome, defined as the rapid development of enlarged, cystic, painful ovaries

Phase II Extension:

- **Stage 1:** Enroll a total of 12 patients (including all treated at the MTD in phase I). *If 5 or more of these respond, the trial will continue to stage 2.*

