Subcutaneously-delivered urinary hCG has safely been given to both men and women for endocrinologic indications, with data regarding safety and efficacy spanning over 4 decades [23, 24, 25, 26, 27]. Severe reactions including arterial thromboembolism and ovarian hyperstimulation syndrome occur in <1% of patients. The doses administered on this protocol are within the range of established standard of care dosing for endocrinologic indications today. Similar low doses of urinary hCG given to a cohort of patients with steroid-refractory chronic GVHD was well tolerated. Therefore, we believe the safety risks of this study are very minimal. However, the

doses required to significantly increase plasma and tissue EGF levels and exert immunologic effects are not known, making the studies proposed herein necessary for further repurposing of the drug.

3 Summary and Rationale

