6.4 Patients Who Do Not Complete All Study Treatments

A patient must receive at least 3 doses of Pregnyl to be evaluable for safety/tolerability in the phase I portion of the study. If a patient receives fewer doses and discontinues study therapy for a reason unrelated to study drug toxicity, the patient will be replaced within their assigned arm, however these patients may re-consent and enroll on the study again if they are eligible at a later time.

In the phase II portion of the study, a patient must receive at least 3 doses of Pregnyl to be assessed for response in Arm 1. In Arm 2A and 2B, a patient must receive at least 6 doses to be assessed for response. If a patient does not complete the number of doses necessary for response assessment, the patient will be replaced within their assigned arm, however these patients may re-consent and enroll on the study again if they are eligible at a later time.

7 Treatment Plan

Patients may remain on their standard of care current acute GVHD therapy, including calcineurin inhibitors, sirolimus, and systemic corticosteroids at the start of study treatment, unless any of these agents are determined to unsafe due to an unforeseen complication.

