7.1 Arm 1 – High-Risk aGVHD

Standard of care immunosuppression, plus Pregnyl® (hCG supplementation) at assigned dose subcutaneously every other day for 4 doses

If a patient has a toxicity that fits the definition of dose limiting as defined in the phase I section below, the patient will discontinue study treatment.

Continue protocol treatment through day 7. Assess response at day 7:

- **If a complete or partial response**, the patient is eligible to receive Pregnyl maintenance at the same dose twice weekly for 10 doses beginning day 9 to 12. Refer to [section 9](#) for response definitions.
- **If no response**, the patient will be taken off study treatment

Pregnyl® dose level assignment will be done by treatment arm, with Arm 1 independent of Arms 2A and 2B.

For phase I, up to 5 dose levels of Pregnyl® will be tested; however dose levels -1 and -2 will be used only if dose level 1 proves too toxic.

Dose Level	Dose
-2	125 USP hCG/875 pg EGF/m ²
-1	250 USP hCG/1,750 pg EGF/m ²
1 (start)	500 USP hCG/3,500 pg EGF/m ²
2	1,000 USP hCG/7,000 pg EGF/m ²
3	2,000 USP hCG/14,000 pg EGF/m ²

The 1st 2 patients will be enrolled in dose level 1. The next cohort of 2 patients will not begin treatment until all patients in the current cohort have reached day 21 in order to assess for dose limiting toxicity (DLT).

Dose limiting toxicity (DLT) is defined as any of the following occurring by day 21 after the 1st dose of Pregnyl® (phase I component only):

- In males and females: Grade 2-4 thromboembolic event (CTCAE v4) i.e., any thrombosis more severe than a superficial venous thrombosis develops and treatment with anticoagulation is required
- In males and females: Grade 3-4 ascites (CTCAE v4)
- Specific to females: Grade 3-4 ovarian hyperstimulation syndrome, defined as the rapid development of enlarged, cystic, painful ovaries - refer to [section 11.2](#) for CTCAE grading guidance

Each new cohort of 2 patients will be assigned by the study statistician to the most appropriate dose level based on toxicity probabilities set for this study. The MTD will be identified when the total sample size of 20 patients is reached.

For the phase II the dose of Pregnyl will be that identified as the MTD during phase I.

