7.5 Duration of Study Therapy

Arm 1 (high-risk aGVHD): Study treatment will be for a minimum of 7 days with study therapy continuing for an additional 5 weeks if a complete or partial response is documented at the initial response evaluation. Non-responders at 7 days will be taken off study therapy and treated at the discretion of the treating physician. The treating physician may remove patients from study participation sooner if concerns regarding safety emerge prior to completing 7 days on protocol.

Arm 2A and 2B (steroid-refractory/dependent aGVHD): Study treatment will be for a minimum of 14 days with study therapy continuing for an additional 5 weeks if a complete or partial response is documented at the initial response evaluation. Non-responders at 14 days will be taken off study

therapy and treated at the discretion of the treating physician. The treating physician may remove patients from study participation sooner if concerns regarding safety emerge prior to completing 14 days on protocol.

An exception to the above is if a patient experiences an event that fits the definition of a dose limiting toxicity (Grade 2-4 thromboembolic event, Grade 3-4 ascites or Grade 3-4 ovarian hyperstimulation syndrome). Study treatment will be permanently discontinued in this situation.

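### Ovarian hyperstimulation syndrome is a DLT at any grade in the synopsis and 13.1 but only at Grade 3-4 in 7.1-7.3, 7.5 and 11.2; 6.4 also leaves a DLT before the third dose unaddressed

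*Combined protocol and SAP*

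**What the plan says.** **No grade limit.** The DLT list in Section 13.1 reads "Specific to females: Ovarian hyperstimulation syndrome, defined as the rapid development of enlarged, cystic, painful ovaries". The schema in the synopsis has the same words. Section 13.1 carries its definition over to Arm 2B by reference. Both lists do grade the other two events: thromboembolism at Grade 2-4 and ascites at Grade 3-4.

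**Grade 3-4 only.** Section 7.1 reads "Specific to females: Grade 3-4 ovarian hyperstimulation syndrome, defined as the rapid development of enlarged, cystic, painful ovaries", and 7.2 and 7.3 match it. Section 7.5, on permanent discontinuation, names "Grade 2-4 thromboembolic event, Grade 3-4 ascites or Grade 3-4 ovarian hyperstimulation syndrome". Section 11.2 also says Grade 3-4 and, because CTCAE does not grade the syndrome, supplies a generic scale from 1 to 4.

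**Collection.** The toxicity row of both Section 10 schedules points to 11.2. The syndrome is not on the 11.2 list of events for the case report form, and the 11.2 DLT list takes it only at Grade 3-4.

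**Evaluability.** Section 6.4 says "A patient must receive at least 3 doses of Pregnyl to be evaluable for safety/tolerability in the phase I portion of the study". It replaces a patient who received fewer doses only if that patient "discontinues study therapy for a reason unrelated to study drug toxicity". Sections 7.1-7.3 and 7.5 stop study treatment at a DLT. Section 13.2 caps phase I at 20 evaluable patients per arm.

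**Thromboembolism.** The grade range is the same everywhere, but its explanation varies: "any thrombosis more severe than a superficial venous thrombosis where treatment is required" in the synopsis, "any thrombosis more severe than a superficial venous thrombosis develops and treatment with anticoagulation is required" in 7.1-7.3, and none in 11.2 or 13.1.

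**The concern.** The binary DLT outcome is all the data the CRM uses. It sets the dose of each new cohort and the MTD carried into phase II. If the clinical staff apply 7.1-7.3 and 11.2 while the statistician applies 13.1, the same patients can give two different DLT counts. If 13.1 governs, the Grade 1-2 cases it counts may never reach the statistician, because 11.2 does not ask for them.

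The 6.4 point is smaller. Read literally, a patient who stops for a DLT after one or two doses is neither evaluable nor replaced. The model could lose exactly the kind of event it exists to count.

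**Working it through.** **Inputs.** From 13.1:
- Model: P(DLT at level i) = p_i^exp(α), with α ~ N(0, variance 2).
- Skeleton for Arms 1 and 2A (levels -2, -1, 1, 2, 3): 0.01, 0.02, 0.05, 0.10, 0.20; target 0.25.
- Skeleton for Arm 2B (levels -2, -1, 1 to 5): 0.01, 0.02, 0.05, 0.10, 0.15, 0.20, 0.25; target 0.30.
- Rule: choose the level whose posterior mean is closest to target, escalating at most one level.

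From 13.2, patients treated at levels 1, 2, 3, all with 0 DLTs: Arm 1 2, 2, 6; Arm 2A 1, 0, 3; Arm 2B 1, 2, 4.

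**Method.** With y_i DLTs among n_i patients, the posterior for α is proportional to exp(-α²/4) × Π [p_i^exp(α)]^y_i × [1 - p_i^exp(α)]^(n_i - y_i). The posterior mean of each toxicity probability is computed on a grid of α.

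**Reproducing 13.2 (0 DLTs).** Arm 1: level 3 (0.034). Arm 2A: level 3 (0.074). Arm 2B: level 5 is closest (0.073), limited to level 4. All three agree with 13.2.

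**Next cohort of 2**, at level 3 in Arms 1 and 2A and level 4 in Arm 2B:

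| Arm | 0 DLTs | 1 DLT | 2 DLTs |
|---|---|---|---|
| 1 | L3 0.027, stay | L3 0.132, stay | L3 0.219, stay |
| 2A | L3 0.049, stay | L3 0.224, stay | L3 0.368, L2 0.254, **move to L2** |
| 2B | L5 0.055, L4 0.041, go to L5 | L5 0.221, L4 0.179, go to L5 | L5 0.337, L4 0.288, **stay at L4** |

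Distances from target with 2 DLTs are 0.004 (L2) against 0.118 (L3) in Arm 2A, and 0.012 (L4) against 0.037 (L5) in Arm 2B. Reading across:
- One disputed event alone (1 counted or 0): no arm's dose changes.
- One disputed event beside one undisputed DLT (2 or 1): Arms 2A and 2B split; Arm 1 does not.
- Two disputed events (2 or 0): the same split.

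These recommendations hold with prior variance 1.34 and with a plug-in estimate at the posterior mean of α.

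**If one of the 4 treated Arm 2A patients were reclassified as a DLT:**
- Event at level 3: L2 0.210, L3 0.312, so distances 0.040 and 0.062, and the dose moves to level 2. This is not robust: the plug-in gives 0.180 and 0.301 (distances 0.070 and 0.051) and stays at level 3.
- Event at level 1: L2 0.278, L3 0.390, so the dose moves to level 2. The plug-in (0.263, 0.393) agrees.

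**If an early DLT had been dropped under 6.4, so one patient is added to those 4 in Arm 2A:**
- At level 3: L2 0.165, L3 0.262; stays.
- At level 1: L2 0.243, L3 0.355; moves to level 2.

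In Arms 1 and 2B, one such event at any level used, reclassified or additional, leaves the posterior-mean recommendation at level 3 and level 4.

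**The case against.** The strongest case is that the working text already points one way. Five sections on treatment, discontinuation and reporting agree on Grade 3-4, only 11.2 supplies a scale, and the schedules send staff there. Conduct is therefore probably more uniform than the text. That makes divergence less likely, but it does not resolve it: 13.1 is the section the statistician follows, and it omits a grade for this event alone while grading the other two.

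The disputed set is also narrow. Every version requires painful ovaries, so an asymptomatic Grade 1 case is not a DLT under 13.1 either. Only mildly symptomatic Grade 1 cases and Grade 2 cases in female patients are in dispute. That stands.

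The effect is limited. One event in the next cohort changes nothing, Arm 1 never moves in the cases tested, and nothing suggests that the zero counts in 13.2 are wrong. Those counts may also be old: the amendment log last mentions Section 13 in October 2017, and the document runs to May 2020. The figures therefore illustrate sensitivity and do not forecast a decision.

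On 6.4, the replacement clause and a DLT window that runs from the first dose both indicate that an early DLT should count. With dosing on days 1, 3 and 5, the gap covers only the first few days. Alone, it would be a clarification. The differing thromboembolic explanations are editorial.

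**Conclusion.** The contradiction is real and in current text. The phase I primary outcome has two definitions that differ for symptomatic Grade 1-2 ovarian hyperstimulation in female patients, and no section says which prevails. The thromboembolism and ascites grades and the day-21 window agree throughout.

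Its size is modest. In the next cohort a dose changes only when two events would be counted under one definition and one or none under the other, and then only in Arms 2A and 2B. For patients already treated, only Arm 2A is sensitive to a single event. These results assume the 13.1 model with posterior means and the 13.2 counts.

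The chance of such a split cannot be given. Section 2 states that "Severe reactions including arterial thromboembolism and ovarian hyperstimulation syndrome occur in <1% of patients", which does not bound lower grades. Section 13.2 records 0 DLTs without saying which definition was applied. The point should be corrected because it concerns the only quantity that drives dose assignment and the correction is cheap. The 6.4 omission is secondary.

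**What to change.** 1. Reconcile the synopsis schema, 7.1-7.3, 7.5, 11.2 and 13.1 to one DLT definition. The clinical team chooses the grade threshold; this review proposes none. Use the same explanation of the thromboembolic grade in each place.
2. Make the 11.2 case-report-form list collect ovarian hyperstimulation syndrome at the grades that definition needs.
3. In 6.4, state that a phase I patient is DLT-evaluable after at least 3 doses, or with a DLT by day 21 after the first dose.
4. Check once against source records that the 0-DLT counts in 13.2 follow the reconciled definition.

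The cost is protocol wording, one form item and that single check. The model, targets and sample size do not change.
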